#### **Six-Month Follow-Up Period**

To evaluate the persistent effects of *Exercising Together* on individual and relationship health, all couples will be followed for an additional 6 months after formal training stops. Couples may wish to maintain their exercise habits or participate in shared activities other than exercise after formal training stops and we will not discourage them from doing so. To provide couples in supervised programs a resource to continue to engage in exercise after supervised training stops we will provide them with a DVD of their programs to use at home. During the last month of supervised training we will prepare participants for the transition to unsupervised training with discussions about behavioral strategies to stay active. We will assess participation in exercise and shared activities at 9 & 12 months and consider these behaviors in analysis for Aim 3 (see **Analysis Plan**). We will also repeat all measures at month 12 in order to better assess the residual effects of *Exercising Together* among couples that do or do not continue to exercise or engage in shared activities in the follow-up period.

**Participant safety.** None of our participants have dropped out of a study due to an injury related to exercise training; however, as with any study in older adults, exercise adherence has been affected by minor musculoskeletal complaints that usually stem from pre-existing orthopedic conditions. We will reduce the risk of injury and symptoms that might limit exercise adherence by: 1) required physician clearance for every participant and 2) monitoring and early care of musculoskeletal symptoms. If a survivor develops metastatic disease during the study his/her data from the point of the diagnosis will be considered separately, but s/he could continue in the study program with physician clearance.

**Participant Incentives:** Remuneration will be provided to couples based on completion of each study related activity as outlined in the table below, at each of the four main time points (baseline, 3-months, 6-months, and 12-months).

To offset travel burden for couples who live outside of the Portland metro area, a \$25 remuneration will be provided at testing visits for couples whose travel exceeds a 60-mile roundtrip. In addition, we will provide added compensation for excess miles driven (outside of the 60-mile roundtrip) using the 2020 standard mileage rate for medical visits of 17 cents per mile. The total travel compensation will not exceed \$100 per testing time point for a maximum total compensation of \$400 per couple. When travel exceeds 150 miles roundtrip, the couple may be provided with one night of hotel accommodations in the OHSU vicinity.

A couple completing only remote testing and surveys will be compensated \$35 per visit, for a total of \$140 over the course of their one year enrollment.

A couple traveling less than 30 miles from OHSU and completing in-person testing, blood draw, and surveys will be compensated \$85 (\$100 with remote testing) per visit, for a total of \$340-\$400 over the course of their one year enrollment.

A couple traveling  $\geq$  60 miles roundtrip from OHSU and completing in-person testing, blood draw, and surveys will be compensated between \$110 and \$185 depending on mileage (\$125-\$200 with remote testing), for a total of \$440-\$800 over the course of their one year enrollment.

Study Activity	Compensation per time point*, per couple
Surveys	\$20
Performance testing – remote	\$15
Performance testing – in-person	\$25
Blood draw	\$40
Travel $\geq$ 60mi roundtrip from OHSU	\$25 + \$0.17/mi outside of 30mi, max \$100 total
Travel $\geq$ 150mi roundtrip from OHSU	1 hotel night

\*Time points: baseline, 3-month, 6-month, and 12-month

Ancillary study: Participants enrolled in the ancillary study will participate remotely and will not be asked to travel, therefore they will not receive remuneration for travel.

Participants in the ancillary study may be provided with a small monthly remuneration (up to \$10 month for 7 months) to help offset costs of broadband and/or cellular services needed to participate.

### **Measures and Data Collection**

Outcomes data will be collected at 0 (baseline, just prior to randomization), 3 (mid-intervention), 6 (post-intervention), and 12 months (6 mos. after completion of the intervention (follow-up)). Written surveys are completed on a computer at the testing facility at baseline and online for follow-up visits. All measures are completed by both members of the couple at each wave.

Primary Outcome Measure:

1. Dyadic coping

Measured by the Relationship Focused Coping Scale to assess the degree with which couples practice active engagement and protective buffering using questions on a scale from 1 (never) to 5 (very often).

[Time Frame: 0 baseline (just prior to randomization), 3, 6, and 12 months]

2. Emotional intimacy

Measured by the Dyadic Adjustment Scale (DAS) to assess each partner's satisfaction with their relationship by answering questions on a 6-point scale ranging from 1(always agree) to 6 (always disagree).

[Time Frame: 0 baseline (just prior to randomization), 3, 6, and 12 months]

3. Physical intimacy

Measured by the Physical Intimacy Behavior scale which asks participants the frequency that they engage in, initiate, and avoid intimate behaviors using questions on a scale from 1 (none of the time) to 4 (most or all of the time).

[Time Frame: 0 baseline (just prior to randomization), 3, 6, and 12 months]

4. Concealment of symptoms

Measured by the Emotional-Intimacy Disruptive Behavior Scale. Patients report the extent to which they engage in 8 behaviors using a scale from 1 (rarely or none of the time) to 4 (most or all of the time).

[Time Frame: 0 baseline (just prior to randomization), 3, 6, and 12 months]

5. Symptom incongruence

Measured by the degree of agreement between the survivor and spouse/partner ratings of the survivor's pain, fatigue and physical function in the past week using the following instruments: the Brief Pain Inventory (BPI) to measure pain intensity and pain interference, Functional Assessment in Chronic Illness Therapy (FACIT) fatigue survey to measure fatigue, and perceived physical function using a subscale of the SF-36 medical outcomes survey (all described below).

[Time Frame: 0 baseline (just prior to randomization), 3, 6, and 12 months]

Secondary Outcome Measure:

6. Body composition

Measured by bone-free lean and fat mass (kg) for the whole body determined from a whole body dual energy x-ray absorptiometry (DXA) (Hologic-QDR Discovery Wi; APEX software, v.4.02) scan and used to calculate the % body fat.

[Time Frame: 0 baseline (just prior to randomization), 3, 6, and 12 months]

7. Cardiovascular health: serum fasting lipids

Measured by serum fasting lipids (total, high-density and low-density lipoprotein cholesterol and triglycerides)

[Time Frame: 0 baseline (just prior to randomization), 3, 6, and 12 months]

8. Cardiovascular health: insulin resistance

Measured by Homeostasis Model Assessment – Insulin Resistance - HOMA-IR: as the product of glucose and insulin, obtained from a fasting blood sample, divided by a constant.

[Time Frame: 0 baseline (just prior to randomization), 3, 6, and 12 months]

9. Cardiovascular health: resting blood pressure

Measured by the average of three consecutive resting blood pressure measurements (systolic and diastolic pressures).

[Time Frame: 0 baseline (just prior to randomization), 3, 6, and 12 months]

10. Inflammation

Measured by serum levels of high sensitivity C-reactive protein (hsCRP) and tumor necrosis factor alpha (TNF alpha) obtained from a fasting blood sample.

[Time Frame: 0 baseline (just prior to randomization), 3, 6, and 12 months]

11. Objective physical function

Measured by the Physical Performance Battery (PPB) to determine a person's ability to perform daily tasks independently. The PPB consists of 3 timed tests: 5 repeated chair stands, standing balance, and gait speed over 4 meters. Each test is scored 0 (unable) to 4 (completes without difficulty), based on quartiles of performance, then scores are summed. The possible range of scores is 0-12.

[Time Frame: 0 baseline (just prior to randomization), 3, 6, and 12 months]

12. Quality of life (QOL): QLQ-C30 and SF36

Measures QOL in cancer patients including subscales of physical and mental functioning. The SF-36 Health Survey assesses QOL in the general population.

[Time Frame: 0 baseline (just prior to randomization), 3, 6, and 12 months]

13. Depressive symptoms

Measured by the Center for Epidemiological Studies-Depression (CES-D) scale to determine the degree of depressive symptoms.

[Time Frame: 0 baseline (just prior to randomization), 3, 6, and 12 months]

14. Anxiety

Measured by the PROMIS anxiety short form using questions on a scale ranging from 1 (never) to 5 (always).

[Time Frame: 0 baseline (just prior to randomization), 3, 6, and 12 months]

15. Fear of recurrence

Measured by the Fear of Recurrence scale to assess the amount of concern survivors have about their cancer returning in the future. Participants respond to questions ranging from 1 (strongly agree) to 5 (strongly disagree).

[Time Frame: 0 baseline (just prior to randomization), 3, 6, and 12 months]

Other Pre-specified Outcome Measures:

16. Sexual function

Measured by the NIH PROMIS® Sexual Function and Satisfaction survey

[Time Frame: 0 baseline (just prior to randomization), 3, 6, and 12 months]

17. Caregiver strain

Measured by the 18-item Multidimensional Caregiver Strain Index and the 6-item Role Overload scale.

[Time Frame: 0 baseline (just prior to randomization), 3, 6, and 12 months]

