Functional Strength Training: The basic training program for all three study arms is a functional strength training program based on recommendations for improving muscle strength in adults [41] and our prior studies in cancer survivors. Participants wear a weighted vest while performing lower body resistance exercises (chair rises, 90° squats, lunges). By wearing weighted vests, functional exercises can be performed without encountering balance-related safety risks from handheld barbells and dumbbells. Participants use free weights (dumbbells and bands) to provide overload for upper body exercises (1-arm row, bench press, push ups, triceps extension, shoulder raise). Volume of resistance exercise, determined by intensity (weight, tailored to each individual) and duration (number of repetitions and sets), is gradually increased from low weight and high repetitions to more weight and fewer repetitions over the training period for continuous overload. Unique features of our strength training program make it particularly suitable to be performed as a partnered program even among training partners who differ in their exercise capacity. We prescribe strength training as a relative intensity so that it can be tailored for each individual. Specifically, the amount of weight placed in vests for lower body exercise is prescribed as a % of body weight, so that untrained individuals with greater body mass, reflective of absolute lean mass, begin with a higher weight than smaller individuals. For upper body exercises, the individually determined amount of weight that a participant can lift the prescribed # of times, or resistance band that a participant can complete a prescribed # of repetitions correctly, will be used to set resistance. Other paired activities, such as dance, require that both partners exercise at the same absolute intensity which likely demands different levels of effort from each individual - creating safety concerns for the partner who is expending greater effort or undertraining partners who are limited by their less fit partner. The initial training progression across the study is based on our prior work and pilot study of *Exercising Together* [39, 42, 43]. Instructors, the Project

Director and [name] will confer on a monthly basis to refine individual participant efforts across arms based on tolerance and to adjust training progression.

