### **Additional Outcomes**

Physical activity (PA): To determine whether or not participation in *Exercising Together* changes overall PA levels and to compare our data against other studies that measure PA by self-report we will administer the 41-item Community Healthy Activities Model Program for Seniors (CHAMPS) PA questionnaire[88]. CHAMPS is a widely used and reliable[89] measure of PA in older adults that we've used in cancer survivors[38, 90-92].

Postural and dynamic stability will also be tested using the Mobility Lab ISWAY test and 6-min walk (APDM, Inc., <http://apdm.com>). The instrumented versions of the 6 min walk test and the Static Balance Test incorporate the use of wearable sensors to electronically detect changes in mobility beyond simple time measures or subjective scales. For each test, participants will wear six watch-sized movement sensors strapped to the wrists, ankles, chest, and waist using Velcro bands. The ISWAY consists of a 30-second trial of standing quietly and captures the amplitude, frequency, velocity and jerkiness of postural sway in multiple directions. This test will be completed once with the eyes open, feet together and once with the eyes closed, feet together. Postural sway is associated with balance control, is a strong predictor of falls, and is worse in those with neurological impairment.Mancini & Horak, 2010

Cancer-related loneliness: Participation in group-based exercise may facilitate development of friendships and comradery with others around a shared experience of cancer, which may result

in reduced feelings of loneliness. To assess changes in cancer-related loneliness, we will administer a validated cancer-related loneliness questionnaire, the Cancer Loneliness Scale Adams, 2017, to survivors. We will administer a modified version of the Cancer Loneliness Scale to spouses/partners in which language referring to the cancer survivor is revised to refer to the cancer survivor's intimate partner. We will administer the CLS and the modified CLS to newly enrolled participants.

**Intervention Feedback:** To better assess program feasibility and acceptability, as well as capture participant experiences not possible from our standardized surveys, we will be administering a survey (Post-Intervention Survey) at the end of the 6-month intervention that includes both qualitative and quantitative questions about the participant's experience in their assigned exercise program.

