##### **Inclusion Criteria: *Survivors and Spouses/Partners:***

- Age 35-80 years (confirmed by self-report on Health History Questionnaire)
- Underactive (< 2 strength training sessions per week, lasting 30 minutes or more per session, at a moderate intensity in the last month) (confirmed by self-report on Health History Questionnaire or by discretion of the Principal Investigator)

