Aims 2: Determine the efficacy of partnered strength training on physical and mental health. Separate longitudinal multivariate-outcomes models will be used to directly examine the effect of partnered strength training in couples on each physical (body composition, lipids, insulin resistance, blood pressure, inflammation, and physical function) and mental health outcome (anxiety, depressive symptoms, fear of recurrence) as described above under Aim 1.

Aim 3: Determine the persistence of Exercising Together. Sustained effects will be tested by comparing linear and quadratic trajectories across time (as discussed above). We will also separately estimate and directly compare the intervention effects between the intervention (baseline to 6 months) and follow-up (6 months to 6 months after end of intervention) periods.

Aim 4: Exploratory analyses: Patterns and predictors of types of couples who benefit the most. GMM identifies distinct patterns of change that vary around different means, have unique variance and homogenous within-trajectory growth. Based on conditional probabilities, cases are assigned to the “most likely class” or pattern of change over time (e.g., couples who benefit/improve most from the intervention). Couple-level estimates from Aims above will be integrated into progressive GMM to determine if there are distinct and naturally-occurring patterns of change in outcomes over time with the dyad as the unit of analysis. Survivor-, spouse/partner- and couple-level

determinants of fitting one pattern of change over the other(s) will be modeled using logistic, multinomial or ordinal regression as appropriate. This integrated multilevel and mixture modeling approach has been used previously by this team,[118] as it allows us to identify types of dyads and differentiate them based on individual and couple-level factors. Finally, based on our pilot, we expect the intervention to have a positive effect on relational outcomes although it is possible that in a larger trial a small subgroup of couples will experience poorer outcomes; identifying characteristics of each common type of couple will allow interpretation of the generalizability of our findings.

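### The PPB cuts timed function tests into capped 0-4 points and no analysis of the times is planned, so Aim 2 gives up sensitivity that the recorded data could supply

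*Combined protocol and SAP*

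**What the plan says.** Secondary outcome 11 in section 3.0 (Measures and Data Collection) describes the battery: "The PPB consists of 3 timed tests: 5 repeated chair stands, standing balance, and gait speed over 4 meters". The scoring rule is "Each test is scored 0 (unable) to 4 (completes without difficulty), based on quartiles of performance, then scores are summed", and "The possible range of scores is 0-12". The text does not say whose quartiles are meant, whether the cut-points are fixed or re-derived at each visit, or whether survivors and partners share them.

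The Aim 2 paragraph of the Analysis Plan fits separate longitudinal dyadic models "on each physical (body composition, lipids, insulin resistance, blood pressure, inflammation, and physical function". Under Aim 1, whose method Aim 2 adopts, the test is a group coefficient on the slope, which is a contrast between arms. No model of chair-stand time or gait speed is mentioned.

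Other objective measures exist. Under Additional Outcomes, "Postural and dynamic stability will also be tested using the Mobility Lab ISWAY test and 6-min walk", and the Schedule of Events places these beside the PPB. One-repetition-maximum strength is a process measure. The remote-visit text in section 3.0 drops all three and keeps the PPB.

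**The concern.** Three performances recorded in seconds become three four-step scores. That loses information in two ways. Someone already at 4 on a test has no room to improve on it, and anyone who improves without crossing a cut-point is recorded as unchanged.

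The setting makes this more than a formality. Eligibility is "Age 35-80 years (confirmed by self-report on Health History Questionnaire", and people who cannot ambulate, cannot stand for 3 minutes or have a severe balance disorder are excluded, which trims the low end of function. The training in every arm also overlaps with a tested task: "Participants wear a weighted vest while performing lower body resistance exercises", and chair rises are listed among them. Some improvement in all arms is therefore plausible, and it pushes people towards the top band.

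At stake is the Aim 2 question of whether partnered training improves physical function more than the comparators. A real difference could be missed through scoring alone, although the times that might show it are already taken.

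**Working it through.** **Plan's own figure.** Three tests at 0 to 4 points give 3 × 0 = 0 to 3 × 4 = 12. The stated range reproduces. The documents give no PPB mean, SD, effect size or share at the maximum, so every performance distribution below is an assumption.

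**Ceiling on one test.** Assume normal performance, cut-points at the baseline quartiles (z = -0.674, 0, 0.674), and a true gain of 0.4 SD for everyone without measurement error. The proportion crossing each cut-point is:

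- Φ(-0.674) - Φ(-1.074) = 0.250 - 0.141 = 0.109
- Φ(0) - Φ(-0.4) = 0.500 - 0.345 = 0.155
- Φ(0.674) - Φ(0.274) = 0.750 - 0.608 = 0.142

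The sum is 0.406 points per person per test. All of it comes from the 75% below the top band: 0.406 / 0.75 = 0.54 points each. The 25% already at 4 gain 0. Over three tests the mean change is 3 × 0.406 = 1.22 points.

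**Cut-points re-derived at each visit.** Among those able to do a test, the mean is then (1 + 2 + 3 + 4) / 4 = 2.5 at every visit. Mean change is 2.5 - 2.5 = 0, against +1.22 on the total with cut-points frozen at baseline.

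**Power to separate two arms.** The planned 264 analysable couples give 264 / 3 = 88 per arm. Assumptions: one person per couple, one follow-up visit, test-retest correlation 0.8, between-test correlation 0.5 in the underlying performance, true arm difference 0.15 SD on each test, two-sided alpha 0.05. The model is follow-up = a + b × baseline + c × arm, testing c, with 3,000 simulated trials per setting.

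| Outcome | No shared gain | 0.4 SD shared gain |
|---|---|---|
| Sum of the three continuous values | 0.79 | 0.79 |
| Quartile points, baseline cut-points | 0.60 | 0.55 |
| Quartile points, cut-points re-derived each visit | 0.60 | 0.61 |
| Fixed external cut-points, 25% in top band | 0.62 | 0.55 |
| Fixed external cut-points, 50% in top band | 0.53 | 0.42 |
| Fixed external cut-points, 80% in top band | 0.29 | 0.20 |

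A second analysis of covariance used correlated tests, kept a balance item in the banded score and took only the two timed tests as comparator. Power was about 0.80-0.90 on the times. It was about 0.69-0.79, 0.59-0.64 and 0.38-0.44 on the score with 25%, 50% and 75% in the top band.

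**Reading the two together.** Taking like ends of the ranges, the loss at 25% runs from 0.80 - 0.69 = 0.11 to 0.79 - 0.55 = 0.24. At 75-80% it runs from 0.80 - 0.38 = 0.42 to 0.79 - 0.20 = 0.59.

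**The case against.** The strongest reply is that the PPB reads as a named battery with a defined purpose: "Measured by the Physical Performance Battery (PPB) to determine a person's ability to perform daily tasks independently". For that purpose a top category may be intended, and replacing the score with a purpose-built composite that leaves out balance would change a pre-specified outcome. This stands, and it is why the 0-12 score should be kept.

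The ceiling is also plausible rather than shown. Participants must be underactive, assistive devices are permitted, and the Background describes spouse caregivers as more prone to mobility limitations. The top-band shares are assumptions. The calculations use one role and two time points, where the plan has a four-visit dyadic model, so the absolute power values do not transfer. The direction of the loss does.

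Four stronger readings are tempting but not supported:

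- **That the rule contradicts its own anchor.** If quartiles come from this sample, about 75% of able participants score below 4 even when all complete the test easily. With fixed external cut-points there is no arithmetic conflict, only loose wording. The documents do not say which applies.
- **That training gains are erased.** This needs quartiles re-derived at each visit, which is nowhere stated. Even then, within-arm change and the Aim 3 trajectories would be distorted while the Aim 2 contrast survives (0.61 against 0.55 with frozen baseline cut-points).
- **That function is measured objectively in no other way.** Sway, the 6-minute walk and strength testing are also collected. They are not numbered secondary outcomes and are lost at remote visits.
- **That the trial's power is undermined.** The sample size was derived for Aim 1, and this is one secondary outcome among many.

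**Conclusion.** The point holds as a loss of sensitivity in one Aim 2 outcome. Capped, banded scoring with no planned analysis of the times makes a difference between arms harder to detect. The illustrative loss in power is about 0.1 to 0.25 if a quarter start in the top band on each test, and about 0.4 to 0.6 if three quarters or more do. These figures rest on assumed normal performance, correlations, effect sizes, top-band shares and alpha. None comes from the documents, and the true loss cannot be known without a baseline distribution.

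The missing source and timing of the cut-points is a secondary gap. It matters most for Aim 3, where re-derived quartiles would hide average change. The change is worth making because the tests are already timed.

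**What to change.** In secondary outcome 11, keep the 0-12 PPB as the pre-specified outcome. State one set of cut-points, fixed in advance and applied at every visit to survivors and partners, and reword the anchor so that the rule has a single meaning.

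In the Aim 2 paragraph, add 5-chair-stand time and 4-metre gait speed as continuous outcomes in the same longitudinal dyadic model. Pre-set the value assigned to a participant who is unable to do the test. Balance stays represented through the 0-12 score.

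This needs no new measurement or visit. It adds two secondary analyses, so the extra multiplicity should be acknowledged when they are reported.
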